10.3 Power and Sample Size

10.3.1 We will initially accrue 10 patients for safety analysis regarding the use of the MSOT device pre- and post-surgery. If there are no grade III-V AEs observed in the patients as defined in CTCAE v5.0 per [Section 8.2](#), we will submit an IDE supplement to request an enrollment expansion for an additional 40 patients, for a total of 50 patients. Up to an additional 55 patients will be accrued (to account for patient dropouts) to enroll 40 patients. Thus, a total of 50 patients will be enrolled and scanned (10 patients in the initial analysis and 40 patients following the interim analysis) in order to gather sufficient data to evaluate the proportion of patients with adverse events that may be associated with the MSOT approach. The MSOT approach is not expected to be related to any adverse events except for a possible slight, reversible reddening and temperature increase of sensitive skin. Nevertheless, this study will allow us to estimate the proportion of unexpected adverse events of grade 3 or higher that are possibly, probably, or definitely related to the MSOT approach. With 50 patients, the upper bound of a 95% Clopper-Pearson exact confidence interval will be less than 20% if the observed rate of adverse events is 8% or less (4 out of 50 or less). We expect that the actual value will be 0 out of 50 – and if this is observed the upper bound of this confidence interval will be 7.1% which would provide a useful upper bound for the potential of adverse events.

The study will be terminated early, after 45 patients in total are enrolled and scanned, if 3 or fewer AEs are observed in the patients scanned by the MSOT device, based on the assumption that the upper limit of the 95% Clopper-Pearson exact confidence interval will be less than 20%. The upper limit of the 95% Clopper-Pearson exact confidence interval will be 7.9%, 11.7%, 15.1% or 18.3% respectively for 0, 1, 2, or 3 observed AEs.

10.3.2 **Interim analysis:** This study will initially accrue 10 patients to identify any potential grade III or IV AEs defined in CTCAE v5.0 per [Section 8.2](#). As yet, no study using MSOT in over 600 patients has observed any grade III or IV AEs^{2,3,14,15}. An interim analysis will be conducted after the first 10 patients. If there are no grade III or IV AEs observed in the patients, we will submit an IDE supplement with preliminary safety data, to request an enrollment expansion to 50 patients. If any grade V AEs occur during the investigation, the FDA will be notified immediately and the study halted for further accrual until discussed with FDA.

10.4 **Estimated Accrual Rate**

10.4.1 The estimated accrual rate is 10-20 patients per month after the initial accrual of 10 patients.

10.5 **Estimated Study Length**

10.5.1 Subjects will be actively enrolled only for the duration of pre-op through surgical recovery, and until post-op discharge unless any study-related adverse event occurs. Medical record review will occur up to 6 months to allow for follow-up pathology assessments to be gathered and provide information to allow for analyses to be performed as previously described.

11.0 **ETHICAL AND REGULATORY CONSIDERATIONS**

11.1 **Ethical Conduct of the Study**

The study will be conducted in full conformance with the ICH E6 guideline for Good Clinical Practice and the principles of the Declaration of Helsinki in addition to the requirements of the ICH E2A guidelines. This study will also comply with U.S. FDA regulations under a U.S. Investigational Device Exemption (IDE) application in addition to local, state, and federal laws.

11.2 **Informed Consent**

The informed consent document will be in compliance with ICH GCP, local regulatory requirements, and legal requirements. The informed consent document used in this study, and any changes made during the course of the study, will be prospectively approved by the IRB of record.

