4.3 Inclusion of Women and Minorities

- Women and individuals of all races and ethnicities who meet the above-described eligibility criteria are eligible for this trial
- The study consent form will also be provided in Spanish for Spanish-speaking participants. Based on population estimates, we expect approximately 52% of participants to be women. Translating this to our expanded sample size estimate of 50, we plan to enroll at least 26 women. We plan to enroll at least 6% Native American, Hispanic/Latino, or African American (N=3). This would result in at least 6 patients of Fitzpatrick Skin Type I, 40 patients of Fitzpatrick Skin Type II-IV, and 4 patients of Fitzpatrick Skin Type V-VI. Because of the population distribution of our area we do not expect to accrue many individuals of Asian/Pacific Islander ancestry.

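### The primary safety interval is written for grade 3 events only although the stated target is grade 3 or higher; separately, the stop at 45 patients makes 0/45 (7.9%), not 0/50 (7.1%), the expected result if it counts that event

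*Protocol*

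**What the plan says.** **Event in the primary interval.** Protocol 10.3.1 gives the aim as to "estimate the proportion of unexpected adverse events of grade 3 or higher that are possibly, probably, or definitely related to the MSOT approach". Protocol 10.1.1 and SAP 7.a define the first analysis, a 95% Clopper-Pearson interval, as pooling unexpected events of grade 3 that are at least possibly related to MSOT. Neither adds grades 4 and 5. Both also say that adverse events will be estimated by grade, type and attribution.

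**Sample size.** Protocol 10.3.1 states: "Thus, a total of 50 patients will be enrolled and scanned". It adds "We expect that the actual value will be 0 out of 50", with an upper bound of 7.1%, and says the upper bound will be "less than 20% if the observed rate of adverse events is 8% or less (4 out of 50 or less"). The next paragraph reads: "The study will be terminated early, after 45 patients in total are enrolled and scanned, if 3 or fewer AEs are observed". It justifies this by an upper limit below 20% and prints limits of 7.9%, 11.7%, 15.1% and 18.3% for 0 to 3 events.

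**Elsewhere.** Protocol 10.2 gives detectable effects for 50 patients and, as a contingency, for 45. SAP 3.b gives the total of 50 and does not mention the stop. Protocol 4.3 bases its recruitment counts on 50: "Translating this to our expanded sample size estimate of 50, we plan to enroll at least 26 women", and "at least 6 patients of Fitzpatrick Skin Type I, 40 patients of Fitzpatrick Skin Type II-IV, and 4 patients of Fitzpatrick Skin Type V-VI".

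**The concern.** The primary interval is meant to bound serious device harm. If the analysis text is followed to the letter, the gravest related events are the ones it leaves out. The SAP repeats the narrower wording, so it does not correct the protocol.

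The stop at 45 fixes the final sample size and the denominator of that interval. It is mandatory in form, and the favourable result that the preceding paragraph expects is what triggers it. The stop sentence does not say which adverse events it counts, or whether it counts events or patients, although the aim in 10.3.1 is the "proportion of patients with adverse events that may be associated with the MSOT approach".

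**Working it through.** **Inputs.** Final sizes 45 and 50, the stop at 3 or fewer events, the 20% criterion and the printed limits all come from protocol 10.3.1. The pooled event comes from 10.1.1 and SAP 7.a.

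**Step 1: reproduce the printed limits.** The two-sided 95% Clopper-Pearson upper limit is the 0.975 quantile of Beta(x+1, n−x). For x = 0 it equals 1 − 0.025^(1/n).

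| x | n = 45 | n = 50 |
|---|---|---|
| 0 | 7.87% | 7.11% |
| 1 | 11.77% | 10.65% |
| 2 | 15.15% | 13.71% |
| 3 | 18.27% | 16.55% |
| 4 | 21.22% | 19.23% |
| 5 | 24.05% | 21.81% |

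The protocol's figures reproduce to within 0.1 point (11.77% is printed as 11.7%). The thresholds are consistent with the 20% criterion: 3 is the largest passing count at 45, and 4 at 50.

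**Step 2: effect of the grade wording.** Suppose one patient in 45 has a related, unexpected grade 4 event and there is no such grade 3 event. The interval as written uses 0/45, upper limit 7.9%. The interval for grade 3 or higher uses 1/45, upper limit 11.8%. With two such patients it is 7.9% against 15.1%.

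**Step 3: effect of the stop.** Assume that it counts the primary event, once per patient, and that no one is enrolled past 45 before the first 45 have been assessed. Then P(stop at 45) = P(X ≤ 3), X ~ Binomial(45, p):

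| True rate p | 0 | 1% | 2% | 5% | 10% |
|---|---|---|---|---|---|
| P(stop at 45) | 100% | 99.9% | 98.8% | 81.3% | 32.9% |

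Reaching 50 then needs at least 4 affected patients among the first 45. At the expected rate of zero the result is 0/45, and the bound moves from 7.1% to 7.9%, a difference of 0.8 points. The matching figures in 10.2 are 0.43 SD, r = 0.40 and a variance ratio of 2.35, in place of 0.4, 0.38 and 2.24.

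**Step 4: does the stop damage the interval?** Enumerate the final outcomes (stop at 45 if X ≤ 3, otherwise continue to 50), apply the nominal interval at the final n, and scan p from 0.0005 to 0.6. Maximum two-sided non-coverage is 5.04%, at p = 0.195. The interval remains usable.

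**Step 5: sensitivity to the counted event.** Protocol 8.0 defines an adverse event without requiring causality. If the stop counted adverse events of any cause, and 10%, 20% or 30% of patients had one (assumed rates; the documents give none), it would fire 33%, 1.3% or 0.01% of the time. Most such trials would reach 50.

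**Step 6: recruitment counts in 4.3.** The skin-type counts sum to 6 + 40 + 4 = 50, so they cannot all be met in 45. The 26 women can be (26/45 = 57.8%), although 52% of 45 is 23.4.

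**The case against.** **On the grade wording.** A reader might infer that grade 4 and 5 events would disappear from the safety results. They would not: both documents also report adverse events by grade. In addition, 10.3.1 makes the expansion request conditional on no grade III-V event in the first 10 patients, and 10.3.2 halts accrual after any grade V event. The example in step 2 therefore mainly concerns a grade 4 event among the 45 − 10 = 35 later patients. What stands is that the primary interval would not count it.

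**On the stop.** A reader might infer that 0/50 to 3/50 cannot occur. The documents do not support that without the three conditions in step 3:
- The event is unnamed. Context favours the primary event, because the stop uses the same interval and the same 20% criterion. But protocol 6.1 and 10.3.1 also speak of events that may result from, or be associated with, MSOT, which would fit events of any grade.
- If events rather than patients are counted, one patient with four events carries the trial past 45.
- Nothing pauses enrolment while the first 45 are followed to discharge. At the 10 to 20 patients a month in 10.4, five more patients take about 8 to 15 days (5/20 to 5/10 of a 30-day month), so some overrun is plausible.

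It is also fair that the 45-patient limits and detectable effects are already printed in 10.3.1 and 10.2. The SAP's safety population is everyone with MSOT readings, so the denominator will follow the number actually scanned. What remains is which set of figures is called expected, an undefined event, and a rule missing from the SAP. The counts in 4.3 are projections that no analysis uses.

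**Conclusion.** The grade mismatch is the main error and needs no assumption: the aim in 10.3.1 and the analysis text in 10.1.1 and SAP 7.a name different events. One related, unexpected grade 4 event in 45 patients shifts the reported upper limit from 11.8% to 7.9%.

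The 45/50 conflict is real but smaller. Under the three conditions above, the result that the protocol expects ends the study at 45, so the expected bound is 7.9% and not 7.1%. A reader might infer that the stop invalidates the interval; with non-coverage of at most 5.04%, it does not.

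Two matters are minor: the 4.3 skin-type counts, and the 10-patient gate, which reads grade III-V in 10.3.1 and SAP 3.b but III or IV in 10.3.2. The gap at the gate is small in practice because 10.3.2 halts accrual for grade V.

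**What to change.** 1. In protocol 10.1.1 and SAP 7.a, change grade 3 to grade 3 or higher.
2. In protocol 10.3.1, state that the stop counts patients with at least one event of a named type, with the sponsor confirming the type. If it is the primary event, restate the expected precision as 0/45, upper bound 7.9%.
3. In protocol 10.2, present the 45-patient figures as the expected case on the same condition.
4. Carry the stop into SAP 3.b.
5. Rescale the 4.3 counts to 45, and have the sponsor reconcile the 10-patient gate wording across 10.3.1, 10.3.2 and SAP 3.b.

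These are text changes, made through the sponsor's amendment route because the study runs under an IDE. No new data are needed: protocol 8.2 already covers grade, attribution and expectedness. The cost is that the headline bound rises from 7.1% to 7.9%. Removing the stop to keep the 50-patient figures is also open to the sponsor, but that changes the design and is more than a correction of wording.

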Appendix A – Imaging and Tissue Data Collection Form

Study Number: OU-SCC-MSOT PID: 0 1 - _____

Investigator: [name] Surgery Date: ____/____/____

1) Tumor or Lymph Node Assessments:

a) Target tissue

Tumor

Lymph Node

b) Standard of care method of imaging

MRI _____ tumor amount

PET _____ tumor amount

CT _____ tumor amount

Other: _____ tumor amount

c) Did patient receive neoadjuvant therapy?

Yes

No

d) MSOT Image acquired?

Yes

No

e) Was an indicator dye used during surgery?

Yes

[figure not shown]
No

f) If an indicator dye used during surgery, please indicate which dye.

Isosulfan Blue IC Green

2) Location of Imaging

a) Please circle the location of the imaging (below) and provide further description as necessary

[https://anatomyclass123.com /](https://anatomyclass123.com/)

b) Erythema post-MSOT Imaging (RTOG)

i. Time after imaging: (hr: min) _____

ii. Grade (RTOG)

- 0 No erythema present
- 1 Follicular, faint or dull erythema, epilation, dry desquamation, decreased sweating
- 2 Tender or bright erythema, patchy moist desquamation, moderate edema
- 3 Confluent, moist desquamations other than skin folds, pitting, edema
- 4 Ulceration, hemorrhage, necrosis

3) Clinical Pathology Assessment

a) Date or diagnosis (month / year):

b) Positive tumor tissue:

Yes No
 c) For Pancreatic melanoma breast HNSCC ovarian (check one) indicate stage at diagnosis (**TNM classification**):

Tx T0 Tis T1 T2 T3 T4
 Nx N0 N1 N2 N3
 Mx M0 M1

d) Tumor subtype (if applicable) _____

4) Skin temperatures

Pre-Surgery MSOT imaging			
Pre-imaging Skin Temperature (°C)		Time	
Post-imaging Skin Temperature (°C)		Time	

Post-Surgery MSOT imaging			
Pre-imaging Skin Temperature (°C)		Time	
Post-imaging Skin Temperature (°C)		Time	

5) Patient Monitoring (*)please note that patients must be monitored daily for adverse events until discharge). Please answer yes or no if Erythema at grade III or higher or change in skin pigmentation occurs.**

Yes No

_____ Post surgery	_____ 8 day
_____ 1 day	_____ 9 day
_____ 2 day	_____ 10 day
_____ 3 day	_____ 11 day
_____ 4 day	_____ 12 day
_____ 5 day	_____ 13 day
_____ 6 day	_____ 14 day
_____ 7 day	_____ 15 day

Discharge date: _____

6) Adverse event. Please answer yes or no if Erythema at grade III or higher or change in skin pigmentation occurs.

Yes No

If yes, please fill out details below:

_____ Erythema _____ Time _____ Date

_____ Changes in skin pigmentation _____ Date

7) MSOT Scan Times:

MSOT Scan Time (hr: mm)	
Select the preset Hb, HbO, IsoBlue, and/or ICG for wavelengths settings	 Check when complete
Pre-Surgery	Scan Start Time: Scan End Time: Total Scan time:
Post-Surgery	Scan Start Time: Scan End Time: Total Scan Time:
TOTAL scan time (Pre-Surgery+ Post-Surgery Scan times)	

Treating Physician Signature: _____ **Date:** ____ / ____ / ____

PI Signature: _____ **Date:** ____ / ____ / ____

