6.0 Study Outcomes and Study Measures

6.1 Primary Outcome

- 6.1.1 Adverse events as characterized by CTCAE v5.0 in patients that may result from MSOT imaging ($\geq 44^{\circ}\text{C}$)¹³
- 6.1.2 Measurement of skin temperature pre- and post-MSOT imaging (pre- and post-surgery 4 measurements total) with a touch thermometer as part of the safety evaluation of the MSOT device. The thermometer will be placed onto the skin until a temperature appears, about 1 minute, and the temperature will be recorded.

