7.0 Study Plan

7.1 Study-Related Activities

Study Procedures

- Upon receipt of a signed consent form, the research study team will generate a unique identification number so that subjects are de-identified for analysis of data. *Any standard imaging measurements will be added in [Appendix A and B](#).* This unique identification number will be used on the case report form ([Appendix A and B](#)).
- Patients will go through standard care procedures to prepare for surgery. Medically established diagnostic procedures will be used to detect tumor and lymph node margins.
- To evaluate the safety of MSOT ([Figure 2](#)), the device will be used to obtain images of the tumor or lymph node margins for investigational use only to compare to clinical pathology and patient's medical record.
- As part of the standard of care surgery preparation for cancer resection for all tumor types, patients will be injected with standard doses of Isosulfan Blue/ Indocyanine (IC) Green for either lymph node or tumor identification as part of the standard surgical procedure. The MSOT device will detect the presence of dye at the standard dose of dye used for surgical evaluation of tissue.

Figure 2 The MSOT Acuity

- Images will be obtained pre- and post-surgery (example simulation of operating room shown [Figure 3](#)). All imaging will be done in a closed surgical patient; no imaging will be performed on an open surgical patient. [name] has been trained in the use of the MSOT Acuity by the manufacturer, and she will be the MSOT operator for all MSOT imaging for this study. [name] will train the surgeon and surgical staff in the proper procedure for using the handheld

[figure not shown]
[figure not shown]
[figure not shown]
[figure not shown]
[figure not shown]
Figure 3: Demonstration of MSOT scanning procedure. A. Handheld detector covered with drape; B. surgeon; C. MSOT Acuity; D. trained MSOT operator.

detector and will maintain training records for this purpose. Only [name] and her research staff will perform post-imaging analysis on the de-identified digital images stored on the MSOT Acuity. The pathologist and clinician will perform all clinical evaluations of tumor samples as well as post-imaging assessment of treatment area and report where indicated on the imaging case report form. MSOT imaging will be for research only and no treatment decisions will be based on the MSOT images obtained.

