13	The MSOT operator will hold the foot pedal until the self-test routine is finished. If the self-test is interrupted by releasing the foot pedal before the system self-test has been finalized, the test routine will need to be performed again.
14	
A blue indicator in the signaling device on top of the system and in the front panel shows that the laser is ready for emission.
 
15	
The MSOT operator will record the self-test completion on the case report form and note the Start scan time.
 
NOTE: THE FOOT PEDAL WILL BE RELEASED ONCE SELF-TEST ROUTINE IS COMPLETE.

16	The MSOT operator will tell the surgical team when the self-test routine has been successfully completed.
17	
The MSOT operator will remove the probe from the magnetic holder to disinfect it using a germicidal disposable wipe (Sani-Cloth AF3, PDI, Orangeburg, NY), ensuring that the entire surface of the probe is moistened with the disinfectant.
 
18	
The MSOT operator will remove a second wipe from the package and repeat the disinfection process, ensuring that the entire surface of the probe is moistened with the disinfectant and allowed to dwell for at least 3 minutes.
 
NOTE: MSOT Operator will note dwell time on Imaging Case Report Form (Appendix A).

19	After the 3-minute exposure time of the disinfectant, the MSOT operator will dry the probe surface with a commercially available, single-use, lint-free, low-germ towel.
20	A member of the surgical team will cover the handheld probe with a single-use ultrasonic probe drape (US.10.150.080, SonoGuard, Promecon GmbH, Hamburg, Germany), which will be the only part of the Acuity device to make contact with the patient, see (Figure 3).
21	Once time-out procedures have been completed, the surgical team will prepare the patient/region of interest on the skin for the initial MSOT scanning.
22	The skin surface will be cleaned following standard procedures. The skin will be dry without any alcohol pooling per manufacturer instructions, then ultrasound gel (#03-034, Aquasonic clear ultrasound gel, Parker Laboratories, Inc., Fairfield, NJ) will be applied to the area to be scanned.
23	The surgeon will place the imaging probe on the prepped skin area to be imaged BEFORE the laser is activated to avoid excess laser radiation.

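### Unlike skin temperature, erythema and pigmentation have no recorded pre-scan observation, so attributing skin effects to MSOT rests on investigator judgement without a baseline

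*Protocol*

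**What the plan says.** **Temperature.** Protocol 6.1.2 makes this a primary outcome: "Measurement of skin temperature pre- and post-MSOT imaging (pre- and post-surgery 4 measurements total) with a touch thermometer". Appendix A, item 4 follows it, with a field "Pre-imaging Skin Temperature (°C" and a matching post-imaging field for both the pre-surgery and the post-surgery scan.

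**Erythema.** Appendix A, item 2b is headed "Erythema post-MSOT Imaging (RTOG". It holds one elapsed time after imaging and one RTOG grade, and does not say which scan it describes.

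**Later skin checks.** Items 5 and 6 share one instruction: "Please answer yes or no if Erythema at grade III or higher or change in skin pigmentation occurs". The daily list in item 5 begins after surgery and runs to day 15. No item records the skin's starting state.

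**Other causes of skin change.** Section 7.1 says of surgery preparation that "patients will be injected with standard doses of Isosulfan Blue/ Indocyanine (IC) Green". Item 1e asks "Was an indicator dye used during surgery" and item 1f asks which dye, but no field records staining of the skin. Table 2, step 22 reads "The skin surface will be cleaned following standard procedures", and it comes before the probe is placed. Step 28 puts the second scan after the incision is closed and repeats steps 16 to 23, so the cleaning is repeated too.

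**How events are counted.** Protocol 10.1.1 and SAP 7a estimate adverse events by grade, type and relatedness. They then pool the grade 3 unexpected events judged at least possibly related to MSOT. Relatedness is a five-level judgement (Section 8.2). Section 8.6 leaves it to the investigator's opinion whether expected reddening exceeds the usual and so becomes an adverse event.

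**The concern.** Mild reddening and a rise in skin temperature are the only device effects the protocol anticipates (Sections 8.1, 8.6 and 10.3.1). Temperature is measured so that each scan has its own baseline; reddening is not. With no control arm, the comparison of a patient's skin before and after a scan is the only internal control available, and for the visible effects the form does not collect it.

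This matters because other causes of skin change are part of the procedure: cleaning, injected dye, and a closed incision under the second scan. Section 8.6 treats reddening as expected for up to 24 hours after surgery, when the wound itself may be red. Item 6 lists a change in pigmentation as an adverse event, although no earlier state is recorded and a blue dye may have been given. Error can go either way: a surgical or dye effect may be called possibly related, or a device effect put down to surgery. A baseline not recorded at the time cannot be recovered later.

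**Working it through.** **Step 1. What the form records and when** (Appendix A)

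| Measure | Before scan 1 | After scan 1 | Before scan 2 | After scan 2 | Later days |
|---|---|---|---|---|---|
| Temperature (item 4) | yes | yes | yes | yes | no |
| Erythema grade (item 2b) | no | one grade in all, scan not stated | no | same single grade | no |
| Erythema grade III or higher, or pigmentation change (items 5 and 6) | no | no | no | from after surgery | to day 15 |
| Dye used, and type (items 1e, 1f) | once per patient, untimed | | | | |

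Temperature has two baselines and two follow-up readings. Erythema has no baseline and one follow-up grade for two scans. Pigmentation has no baseline. Table 2 contains no skin grading step, and the SAP adds none.

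**Step 2. Which primary estimates are exposed**

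The breakdown by grade, type and relatedness takes in skin events of any grade once they are called adverse events, and the relatedness call is made without a pre-scan observation.

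The pooled rate is narrower. An event enters it only if it is grade 3 (10.3.1 says grade 3 or higher), unexpected, and at least possibly related. On the form's own scale, grade 3 is confluent moist desquamation with pitting edema. Ordinary wound redness or dye staining does not fit that description.

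**Step 3. Size, if such an event is misattributed**

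The Clopper-Pearson upper 95% limit for x events in n patients is the 0.975 quantile of Beta(x + 1, n − x). For x = 0 it reduces to 1 − 0.025^(1/n).

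The plan's own figures (10.3.1) first:
- n = 50, x = 0: 1 − 0.025^(1/50) = 7.11% (printed 7.1%).
- n = 50, x = 4: 19.23% (stated as below 20%).
- n = 45, x = 0, 1, 2, 3: 7.87%, 11.77%, 15.15%, 18.27% (printed 7.9%, 11.7%, 15.1%, 18.3%).

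All agree to within 0.1 percentage point.

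The effect of one patient:
- Point estimate at n = 50: 1/50 = 2 percentage points.
- Upper limit from the expected result: 0/50 gives 7.11% and 1/50 gives 10.65%, a shift of 10.65 − 7.11 = 3.54 points.

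The same shift applies in reverse if a true device event is put down to surgery. The documents give no misattribution rate, so no expected bias can be calculated.

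**The case against.** The best defence is that attribution is already provided for. Section 8.2 has five levels, and Section 7.1 assigns post-imaging assessment of the treatment area to the pathologist and clinician. The form records dye use, dye type and imaging site. Tattoos over the site and local infection are excluded (Section 4.2). Adverse event descriptions go into REDCap, whose other forms are not in the documents. This stands as far as it goes: separation is not impossible. But the attribution levels only name categories, and nothing shown gives the assessor a pre-scan observation for choosing among them.

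A reader might infer more than the documents support:

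- *That wound redness and blue staining distort the headline rate.* The grade 3, unexpected and relatedness conditions keep most such findings out of it.
- *That one misattributed patient breaks the 20% criterion.* The limit does pass 20% at 5/50 (21.81%) and at 4/45 (21.22%), but only if four or three other countable events have already occurred. The protocol expects none.
- *That the expansion and early-termination rules are put at risk.* Neither carries a relatedness condition, so better attribution evidence would not change their count. That is a separate matter.
- *That the interval between first scan and incision goes unrecorded in every patient.* Item 2b may be completed then. The form does not require it or show that it was. Nor is MSOT the only new exposure in that interval, since cleaning comes before scan 1 and dye may do so as well.

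**Conclusion.** The point holds in a limited form. Appendix A gives temperature a reading before and after each scan, but gives erythema one unlinked post-imaging grade and pigmentation no starting state. Telling an MSOT skin effect from skin preparation, dye or incision therefore relies on judgement under Sections 8.2 and 8.6 without a recorded pre-scan observation.

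The main effect is on the primary adverse event estimates by grade, type and relatedness, and the documents do not allow it to be quantified. The pooled rate is affected only through a misattributed grade 3 unexpected skin event, at 2 percentage points per patient at n = 50. This rests on the two appendices, Table 2 and the SAP being the complete plan for skin assessment; a REDCap form with a pre-scan skin field would narrow the point. It is an inexpensive improvement to data collection and does not undermine the safety conclusion.

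**What to change.** In Appendix A, item 4, add two entries beside each of the four temperature readings: an erythema grade, and a yes/no for pigmentation change or dye staining.

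- Take the pre-surgery baseline after skin preparation and any dye already given, but before the probe is applied.
- Take the reading after the first scan before incision.
- Add these moments to Table 2, which at present has no temperature or skin-grading step.

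In Protocol 10.1.1 and SAP Section 7, add a sentence stating that an acute skin effect is worsening from the reading just before that scan, reported separately for the two scans and used to support attribution under 8.2.

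The cost is a brief skin check at four time points that already exist, by whoever already assesses the site. The documents do not say who takes the temperature, so the form should name the role. No new visit or procedure is needed. The change covers acute effects only and does not resolve attribution in the daily checks to day 15.
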